 - Aspartate aminotransferase (AST) $< 1.25 \times \text{ULN}$
 - Alanine aminotransferase (ALT) $< 1.25 \times \text{ULN}$
 - Calculated creatinine clearance (CrCl) $\geq 60 \text{ mL/min}$ as estimated by the Cockcroft-Gault equation:
For men, $(140 - \text{age in years}) \times (\text{body weight in kg}) \div (\text{serum creatinine in mg/dL} \times 72) = \text{CrCl (mL/min)}^*$
*For women, multiply the result by 0.85 = CrCl (mL/min)
- NOTE:** A program to assist in calculations is available on the DMC website at: <http://www.fstrf.org/ACTG/ccc.html>
- Fasting or non-fasting triglyceride level $\leq 350 \text{ mg/dL}$
 - Fasting or non-fasting LDL $< 160 \text{ mg/dL}$
 - Urine protein to urine creatinine ratio $\leq 1 \text{ g/g}$ from random urine collection

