6.2.3 Post-Entry Evaluations

Prior to starting sirolimus, laboratory measurements from the week 12 visit must be assessed to ensure that the criteria detailed in section 4.1.6 and 4.1.10 continue to be satisfied, as well as week 12 CD4+ cell count >300 cells/mm³. If any criterion is not satisfied, the study team should be promptly contacted and sirolimus should not be started. In addition, concomitant medications must be re-assessed at the week 12 visit to ensure that the **participant** has not received any prohibited medications since study entry. If so, the study team should be promptly contacted and sirolimus should not be started.

Participants must begin study treatment within 72 hours after receipt of results from the study week 12 evaluations.

Site staff is encouraged to contact **participants** at least 14 days prior to scheduled study visits (not PK-only visits) to remind **participants** not to receive any vaccinations prior to their visit. A reminder can also be given that prohibited medications are not allowed at any time while on study.

For stored samples, all sites must have established procedures for regular reconciliation and verification of specimens, which must be followed throughout the study per the Lab Processing Chart (LPC). Collection of sample aliquots is of particular importance at the pre-sirolimus time points (entry and week 12) and at the study week 32 time point. In the event that the required volume or number of sample aliquots is not obtained at any time point, designated site clinic and/or lab staff must immediately inform the study team, who will provide guidance on how to respond to the problem.

In addition to following this guidance from the study team, designated site clinic and lab staff will work together to document the problem, take appropriate corrective and preventive action, and document all action taken. Reconciliation must be performed for all specimen types that are received by the laboratory and stored in the LDMS.

For other evaluations, if an evaluation is not completed at a scheduled visit, effort should be made to obtain the evaluation as soon as possible. If unsuccessful, complete the evaluation at the next study visit if not already included as part of the regularly scheduled visit.

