6.3.5 Laboratory Evaluations

Refer to the A5337 Laboratory Processing Chart (LPC) posted on the PSWP for processing, shipping, and storage information.

The screening and entry protocol-required laboratory values, regardless of grade, must be recorded. For post-entry assessments, record **on the CRF and key within 48 hours**, lipid values, glucose, hematology, liver function tests, calculated CrCl, serum creatinine values regardless of grade and all other Grade ≥ 3 laboratory values. In addition, record **on the CRF and key within 48 hours** all laboratory values regardless of grade that led to a change in study treatment or a change in ART. All Grade 3 or higher laboratory values, any laboratory value regardless of

grade that led to a change in study treatment, or that met ICH, EAE or SAE guidelines, are defined by the protocol as reportable events that will require more detailed event reporting and keying within 48 hours.

Hematology

Hemoglobin, hematocrit, white blood cell count (WBC) with differential, absolute neutrophil count (ANC), platelets.

Liver Function Tests

Total bilirubin, direct bilirubin, indirect bilirubin, albumin, AST (SGOT), ALT (SGPT), alkaline phosphatase, creatine kinase (CK).

Blood Chemistries

Glucose, triglycerides, cholesterol (total, LDL), electrolytes (e.g., sodium, potassium, chloride, bicarbonate), lactate dehydrogenase (LDH), creatinine, blood urea nitrogen (BUN), total protein, albumin, globulin (globulin may need to be calculated from the total protein and albumin). Lipid levels may be drawn non-fasting (see section 7.2.5 for management of elevated levels).

Calculated CrCl

Estimated each time that a serum creatinine level is determined. To estimate calculated CrCl, use the Cockcroft and Gault equation (see section 4.1.10).

Urinalysis

Random urinalysis for urine protein to urine creatinine ratio.

Pregnancy Test

For women with reproductive potential: At screening (before chest x-ray) negative serum or urine pregnancy test with a sensitivity range of ≤ 25 mIU/mL, 48 hours prior to study entry and again at week 12 with results available before initiation of study drug, and at any time during the study when pregnancy is suspected.

Hepatitis Serology

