7.2.4 Nephrotoxicity

Any **participant** with a calculated CrCl $<50 \text{ mL}/\text{min}$ or a reduction in CrCl by 30% or more should have the value confirmed within 7 days. Sirolimus will be discontinued if confirmed calculated CrCl decreases by $>30\%$ after initiation of treatment or falls below $50 \text{ mL}/\text{min}/1.73 \text{ m}^2$.

Urine protein to creatinine ratios will also be checked per the SOE. Sirolimus will be discontinued if the ratio is $>1 \text{ g/g}$.

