9.5 Monitoring

Accrual, baseline characteristics, conduct of the study (including premature treatment and study discontinuations, and reasons, and summaries of sirolimus dosages and trough levels), interruptions of ART >2 days, virologic failures (defined as HIV-1 RNA >200 copies/mL on two consecutive assessments), two consecutive CD4 counts below 300 cells/mm³ (or >50% decrease from study entry) and all reported toxicities and events will be monitored during the study with reports sent to the core team on a regular basis. In addition,

assessment of the availability of stored samples for planned assays will be reviewed regularly. The core protocol team will review the individual safety data frequently (at least monthly) to assess relation of all reported toxicities and AEs to study treatment, including in this assessment the site investigator's opinion on their relation to study treatment as reported on the case report forms.

At the earlier of a) approximately 6 months after the first **participant** begins study treatment and b) after 12 **participants** have reached 12 weeks of study treatment, a Study Monitoring Committee (SMC) will be convened to review the study data and progress according to ACTG Standard Operating Procedures. The SMC will review accrual, **participant** characteristics, AE summaries (and listings detailing each team decision as to the relationship of the AE to study treatment), sirolimus dosages and trough levels (in particular for any **participant** with a Grade 3 or higher AE), CD4+ cell counts and HIV-1 RNA levels/suppression over time, off-treatment and off-study rates (and reasons) and completeness of sample availability. In addition, sirolimus use in all **participants** will be stopped and an SMC safety review will be promptly convened if there are any Grade 4 AEs or greater than three Grade 3 AEs attributed to study treatment in two or more **participants** per section 9.2.1.1. An SMC review will also be triggered if more than 25% of **participants** (evaluating at least 12 **participants**, e.g., greater than 3 of 12) discontinue study treatment due to AEs or other side effects attributable to study drug; the therapeutic duration of the trial might be reduced to 12 weeks or otherwise modified following SMC review. Subsequent SMC reviews will be approximately every 6 months. In addition, the core team or the SMC, at any time it thinks appropriate, may ask for the SMC to independently review all available safety data.

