5.3 Visit Schedule and Definition of Week for Analysis Purposes

The visit schedule for key study outcomes is shown in Table 1.

The protocol requires evaluations to be scheduled at the **treatment week 0** visit, ± 1 day at the **treatment week 1, 2 and 4** visits, ± 1 week at the **treatment week 8, 12 and 20** visits, and ± 2 weeks at the **treatment week 32*** visit. The analysis window for post-entry visits will be calculated based on the number of **weeks** since the initial dose of sirolimus and broader windows will be used (as compared to the protocol specified window) in order to minimize the impact of deviations from the desired schedule. If there are multiple evaluations within the window for a given visit, then the evaluation closest to the scheduled study week will be used (and the later measurement will be used if there are two measurements which are equally distant from the scheduled week). Table 1 **below** details the **analysis windows for clinical data**.

For the primary and secondary outcome measures, and the exploratory soluble marker outcome, a database review was conducted by the study chair to identify the time points to be tested based on the availability of samples and the duration of sirolimus use. This resulted in a total of 159 time points for 29 study participants.

- For 16 participants with the full 20 weeks of sirolimus use who will constitute the primary efficacy population: treatment weeks -12, 0, 4, 12, 20 and 32*
- For the 13 participants with at least 6 but less than 20 weeks of sirolimus use: treatment weeks -12, 0, 4, 12 and 20*

Note: One participant went off study early and only has weeks -12, 0 and 4.

Note: Treatment weeks 32* and 20* refer to time points after sirolimus discontinuation. Data from these time points will be used to assess durability of treatment effects and will not be included in the as-treated analysis of efficacy.

Table 1: Study Visit Schedule and Analysis Windows

Evaluation	Screening	Entry	Sirolimus Initiation	Post-Entry Evaluations						
	Treatment Week	-12	0	1	2	4	8	12	20	32
Analysis Window (Weeks Post-Sirolimus Initiation)		0	(0 – 1]	(1 – 3]	(3 – 6]	(6 – 10]	(10 – 16]	(16 – 26]	(26 – 37]	
Clinical Assessment	X	X	X	X	X	X	X	X	X	X
Hematology	X	X	X	X	X	X	X	X	X	X
Liver Function Tests	X	X	X	X	X	X	X	X	X	X
Blood Chemistry	X	X	X	X	X	X	X	X	X	X
Calculated Creatinine Clearance	X	X	X	X	X	X	X	X	X	X
Urinalysis	X		X			X	X	X		
CD4+/CD8+	X	X	X		X	X	X	X	X	X
Plasma HIV-1 RNA	X	X	X			X	X	X	X	X

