13.1 Primary Safety Analysis

All participants who have been exposed to study treatment will be included in the **safety** analyses.

For the primary safety analysis, \geq Grade 3 AEs attributed to study treatment and confirmed CD4+ declines (see **protocol** section 9.2.1.1) will be summarized (including listing of events).

In addition, all reported AEs \geq Grade 3 (regardless of treatment relatedness) will be summarized (**listing**) and a table showing the maximum (for each participant) grade event attributed to study treatment.

Listings identifying the following:

Event description, grade, **lab value and units, treatment week of event**, and relationship to study treatment (as judged by the core team) that occurs any time from the initial dose of sirolimus to the end of study follow-up.

Similar listings restricted to lipids, glucose and creatinine, respectively.

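### Protocol 7.2.4 prints the absolute renal stop in mL/min/1.73 m², but its own trigger and the entry floor are in unindexed mL/min

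*Protocol*

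**What the plan says.** Protocol 7.2.4 has two steps. A participant whose calculated CrCl is under 50 mL/min, or has fallen by at least 30%, "should have the value confirmed within 7 days". Then: "Sirolimus will be discontinued if confirmed calculated CrCl decreases by" more than 30% after treatment starts, or if it goes under 50 mL/min/1.73 m². The first 50 is in mL/min; the second is indexed to body surface area.

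Elsewhere CrCl is unindexed:

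- Protocol 4.1.10 requires at least 60 mL/min at entry, "as estimated by the Cockcroft-Gault equation", and prints the formula with its result in mL/min.
- Protocol 6.2.3 reapplies that floor before the first dose: week 12 laboratory values "must be assessed to ensure that the criteria detailed in section 4.1.6 and 4.1.10 continue to be satisfied".
- Protocol 6.3.5 covers values on study: "To estimate calculated CrCl, use the Cockcroft and Gault equation", with a reference back to 4.1.10.

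Height is recorded at entry and weight at entry and later visits (Protocol 6.3.4), so indexing would be possible. Neither document asks for it or gives a BSA formula, and the clarification memo text provided does not change 7.2.4.

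**The concern.** This is a mandatory safety stop, so it should use the same quantity as the trigger that feeds it. For a participant with BSA below 1.73 m², indexing raises the number. A value low enough to trigger confirmation, and then confirmed, could therefore sit above the printed stop. If the fall is also no more than 30%, 7.2.4 gives no CrCl-based instruction to stop, although CrCl is confirmed below 50 mL/min. Participants of this size are in scope: the dosing tables in Protocol 5.1 start at 50 kg.

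**Working it through.** The 50 in 7.2.4 is a chosen threshold, not a derived figure, so there is no calculation of the plan's to reproduce. The check is to find when the two readings give different instructions.

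**Inputs.** From the protocol: trigger below 50 mL/min; stop limbs of a fall above 30%, or below 50 mL/min/1.73 m² (7.2.4); pre-treatment floor of 60 mL/min (4.1.10 and 6.2.3). Assumed: heights; BSA by Mosteller, √(cm × kg / 3600); and the pre-treatment value as reference for the 30% fall, since 7.2.4 names none.

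**Conditions.** Let C be the confirmed CrCl in mL/min, with C < 50, and B the pre-treatment CrCl.

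- The printed absolute limb is missed if C × 1.73 / BSA ≥ 50, that is, C ≥ 50 × BSA / 1.73.
- The relative limb is missed if (B − C) / B ≤ 0.30, that is, C ≥ 0.7 × B.
- Both are missed when C lies from max(50 × BSA / 1.73, 0.7 × B) up to 50.
- This band exists only if BSA < 1.73 and B < 50 / 0.7 = 71.4. With the floor, B runs from 60 to about 71.
- At BSA of 1.73 or more, the indexed value is no higher than the unindexed one, so any confirmed value below 50 mL/min meets the stop on either reading.

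**Band of confirmed values (mL/min) that miss both limbs:**

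| Weight, height | BSA (m²) | Printed stop in mL/min | B = 60 | B = 64 | B = 66 | B = 68 | B = 70 |
|---|---|---|---|---|---|---|---|
| 50 kg, 160 cm | 1.491 | 43.1 | 43.1–50 | 44.8–50 | 46.2–50 | 47.6–50 | 49.0–50 |
| 55 kg, 160 cm | 1.563 | 45.2 | 45.2–50 | 45.2–50 | 46.2–50 | 47.6–50 | 49.0–50 |
| 60 kg, 165 cm | 1.658 | 47.9 | 47.9–50 | 47.9–50 | 47.9–50 | 47.9–50 | 49.0–50 |
| 65 kg, 165 cm | 1.726 | 49.9 | 49.9–50 | 49.9–50 | 49.9–50 | 49.9–50 | 49.9–50 |

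**Example.** At 50 kg and 160 cm, CrCl falls from 60 to a confirmed 45. The fall is (60 − 45) / 60 = 25%, and the indexed value is 45 × 1.73 / 1.491 = 52.2. The trigger is met and neither stop limb is. With the stop in mL/min, 45 < 50 and sirolimus stops.

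**Starting from the confirmed value.** A confirmed 45 escapes the relative limb only if B is at most 45 / 0.7 = 64.3; a confirmed 48 only if B is at most 48 / 0.7 = 68.6. At BSA 1.491 and B = 60, the fall must lie between (60 − 50) / 60 = 16.7% and (60 − 43.1) / 60 = 28.2%. At B = 70 it must lie between 28.6% and 30%.

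**Large BSA.** Here the printed unit errs in the stricter direction. At BSA 2.0 the printed stop equals 50 × 2.0 / 1.73 = 57.8 mL/min. At 90 kg and 180 cm (BSA 2.12) it is about 61 mL/min, above the entry floor. A participant eligible at 60 would index to 60 × 1.73 / 2.12, about 49, already below the stop before the first dose. The absolute trigger would not send values between 50 and that limit for confirmation, so the practical effect is small, but the printed unit conflicts with the entry criterion too.

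**With the stop in mL/min**, every confirmed value below 50 meets it, and the band is empty at any BSA and any starting value.

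**The case against.** The strongest reply is that the protocol nearly settles the meaning itself. The stop refers to a confirmed calculated CrCl, that term is defined only as unindexed Cockcroft-Gault, and no indexing step is supplied. A site following the text has one number to compare with 50, and on that reading there is no gap. The absurd result at large BSA is further evidence that the suffix is a slip. All of this stands as an account of probable intent and practice. It does not make the printed unit right: a mandatory stop should not depend on sites disregarding part of it.

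Other safeguards could also act: the stop for a urine protein ratio above 1 g/g, the core team's review of individual safety data at least monthly (Protocol 9.5), and possibly the Grade 3 hold in 7.1.2. But the urine ratio does not measure clearance, and the monthly review is not a stopping rule. The Grade 3 hold exempts matters covered in later sections, and its grading cut-offs are not in the documents, so its effect here cannot be checked.

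Finally, the reporting step overlaps with the SAP. Section 12.1 lists graded safety events with laboratory values and units, and section 9 lists reasons for stopping sirolimus early. That is fair, and it keeps the request small. Neither listing, however, is set up to show a participant confirmed below 50 mL/min who stayed on drug.

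**Conclusion.** The concern holds as a minor correction to a safety rule. The unit mismatch is certain from the text. Its consequence is narrow: it needs the literal reading, BSA below 1.73 m², pre-treatment CrCl of 60 to about 71 mL/min, and a confirmed value in a band 6.9 mL/min wide for a 50 kg, 160 cm participant starting at 60. That band shrinks to about 0.1 mL/min at 65 kg and 165 cm. These widths rest on assumed heights and on taking the pre-treatment value as reference for the 30% fall. The documents give no frequency for these conditions; in a 30-person trial few participants, possibly none, would be affected. Nothing here shows that anyone was harmed, and sample size, power and the evaluable count are not involved.

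**What to change.** If the protocol is reissued, state the absolute stop in 7.2.4 as below 50 mL/min by Cockcroft-Gault, citing 4.1.10 and 6.3.5. That changes one phrase.

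Dosing appears complete, since SAP 5.3 already groups 29 participants by duration of sirolimus ("For 16 participants with the full 20 weeks of sirolimus use", and 13 with less). The useful step now is therefore in the safety report. State which unit was applied. SAP 13.1 already plans "Similar listings restricted to lipids, glucose and creatinine, respectively": add calculated CrCl in mL/min to the creatinine listing and mark any participant confirmed below 50 mL/min who continued sirolimus. If there was none, say so.

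The cost is one sentence and one added column. Protocol 6.3.5 already requires calculated CrCl to be recorded regardless of grade, and it is scheduled at each visit, so no new data are needed.

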7.2.5 Hypertriglyceridemia/Hyperlipidemia

Elevated triglycerides or lipid levels Grade ≥ 3 from a non-fasting blood draw should be repeated after an 8-hour fast. Only levels done in a fasting state should be used

to determine toxicity management. **Participants** with asymptomatic Grade <3 triglyceride, total cholesterol, or LDL cholesterol elevations may continue study drugs, at the discretion of the site investigator. See sections 7.1.2 and 7.1.3 for management of Grade 3 and 4 toxicities.

7.3 Management of HPV-Related Disease

Management of anal HPV-related disease is at the discretion of the **participant's** primary care physician, but if at all possible, treatment of anal dysplasia should be delayed until the end of the study.

7.4 Pregnancy Outcomes and Obstetrical History Reporting

Female **participants** who become pregnant while on study must discontinue study medication and study evaluations, but will be encouraged to remain on study so that pregnancy outcome data can be collected. Women will remain on study and complete the premature study discontinuation visit 1 week after stopping treatment; the off-study CRF must be completed at the end of the pregnancy. The outcome and the AEs for the participant and infant will be recorded on an outcome CRF. If a woman does not wish to remain on study follow-up at the time of study discontinuation, site staff should request permission to contact her regarding pregnancy and infant outcomes at the end of pregnancy. If the information is obtained, pregnancy outcomes for the participant and infant will be submitted.

Pregnancies that occur on study in participants receiving ART should be reported by the CRS to the Antiretroviral Pregnancy Registry. More information is available at www.apregistry.com. [contact]; [contact].

8.0 CRITERIA FOR DISCONTINUATION

8.1 Permanent and Premature Treatment Discontinuation

- Drug-related toxicity (see section 7.1 and 7.2).
- Requirement for prohibited concomitant medications (see section 5.4).
- Completion of treatment as defined in the protocol.
- Pregnancy or breastfeeding.
- Request by **participant** to terminate treatment.
- Clinical reasons believed life threatening by the physician, even if not addressed in the toxicity section of the protocol.
- Any two consecutive CD4+ cell counts <300 mm³ or >50% decrease from study entry value.
- Any two consecutive HIV-1 RNA levels >200 copies/mL.
- **Participant** repeatedly noncompliant missing >3 doses of study drug a week for 2 or more weeks.
- **Participant** misses two consecutive PK monitoring blood draws.

- **Participant** misses two consecutive clinic visits.

8.2 Premature Study Discontinuation

- ART is permanently discontinued.
- Request by the **participant** to withdraw.
- Request of the primary care provider if s/he thinks the study is no longer in the best interest of the **participant**.
- **Participant** judged by the investigator to be at significant risk of failing to comply with the provisions of the protocol as to cause harm to self or seriously interfere with the validity of the study results.
- At the discretion of the IRB, NIAID, Office for Human Research Protections (OHRP), and other government agencies as part of their duties to ensure that research **participants** are protected or the industry supporter or its designee.

9.0 STATISTICAL CONSIDERATIONS

9.1 General Design Issues

A5337 is a phase I/II open-label, single-arm, pilot study to evaluate the safety, immunologic, virologic and pharmacologic effects of sirolimus in HIV-infected participants receiving effective ART who have HIV-1 RNA <40 copies/mL and CD4+ T-cell counts ≥ 350 cells/mm³. Each **participant** will receive 20 weeks of sirolimus starting 12 weeks after study entry, followed by an additional 12 weeks off sirolimus, for a total duration of 44 weeks. Sirolimus will be dose-adjusted based on frequent measurements of sirolimus drug levels to achieve desired target levels. Accrual of the targeted 30 **participants** is anticipated to take 8-12 months. Note that the primary outcome measures are through week 32 while the study has an additional 12 weeks of post-treatment follow-up.

9.2 Outcome Measures

9.2.1 Primary Outcome Measures

9.2.1.1 Safety

Occurrence of a new Grade ≥ 3 AE, including signs/symptoms, lab toxicity or clinical event, that is definitely, probably or possibly related to study treatment, as judged by the core team, or by change (confirmed $>50\%$ decline or to <300 cells/mm³) in CD4+ cell counts while on sirolimus.

